3.2.2 Secondary Outcome Measures

- Incidence of hospitalization or death
- Incidence of confirmed SARS-CoV-2 detection
- Incidence of symptoms compatible with COVID-19 (possible disease)
- Incidence of all-cause study medicine discontinuation or withdrawal
- Incidence of adverse reactions
- Symptom severity on day 5 or 14 via visual analog scale
- Ordinal Scale of COVID-19 Disease Severity at day 14 (among those who are symptomatic at trial entry)
 - Illness without hospitalization
 - Hospitalization (or post-hospital discharge)
 - Hospitalization with ICU stay or Death

Assessment of outcome measures will be primarily by self-report. As necessary, COVID19 disease will be verified from public health records, medical records, or death certificates. The primary endpoints are different for the two cohorts (those who are asymptomatic with known exposure; or those who are symptomatic at trial entry), and analyses will be done separately for the two cohorts.

The primary analysis will use PCR+ confirmed disease. However if the absence of sufficient testing supplies continues then outpatients will not be offered SARS-CoV-2 testing unless they are sick enough to be hospitalized. In that case an alternate a priori planned analysis will define incident COVID19 disease as a composite of SARS-CoV-2 PCR+ confirmed result OR symptomatic disease (i.e. possible) COVID-19 in those without testing.

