11.2 Sample Size Considerations

Two cohorts of 1500 subjects each:

- 1) Asymptomatic persons exposed to COVID-19 disease (750 in placebo, 750 in intervention);
- 2) Symptomatic outpatient COVID-19 disease (750 in placebo, 750 in intervention).

Assuming 90% power, a two-sided alpha = 0.05 and loss to follow-up up to 20%, for each cohort the planned sample size is 750 participants per arm based on the following assumptions:

- 10% transmission rate from COVID-19 cases to close contacts
- For those with symptomatic illness the proportions at day 14 in the placebo group are 90%, 8% and 2%, respectively for illness without hospitalization, hospitalization with ICU stay or death, and hospitalization with an ICU stay or death.

The estimated transmission rates are uncertain. Table 1 below (for the asymptomatic cohort with exposure) shows that we are well powered to detect even a smaller (40%) relative reduction in the incidence of COVID 19 with 80% power for transmission rates of at least 10% with placebo. Table 2 (for the symptomatic group) shows that we are well powered to detect a common odds ratio of 0.6-0.75 under the assumption that the control proportions for illness without hospitalization, hospitalization without ICU stay or death and hospitalization with ICU stay or death are 90%, 8% and 2%, respectively.

Table 1. Sample Size Table for Asymptomatic Participants (Healthcare worker or household contact) With Exposure

Estimated transmission rate with placebo	Estimated transmission rate with drug	Percent relative reduction in transmission rate	Sample size (per arm) with 90% power	Sample size (per arm) with 80% power
10%	5%	50%	621	474
	6%	40%	1014	771
12%	6%	50%	509	389
	7.2%	40%	831	632
15%	7.5%	50%	398	304
	9%	40%	648	493

Table 2. Sample size table for participants with symptomatic disease, assuming that the control proportions are 90% illness with no hospitalization, 8% hospitalization with no ICU stay or death and 2% hospitalization with ICU stay or death.

Log Odds Ratio	Odds Ratio	Sample size (per group) with 90% power	Sample size (per group) with 80% power
0.60	1.82	805	601
0.65	1.91	697	521
0.70	2.01	610	456
0.75	2.12	539	403

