- d. The primary outcome will be presented by subgroups formed by COVID test results (confirmed positive vs. other), age groups (18-35, 36-50, > 50), sex, and days from exposure onset to entry. These are apriori subgroups defined in the Version 1.0 of the protocol.
- e. Medication adherence is captured on study day 5. Another subgroup of interest is comparing the treatment groups for change in symptom severity score after day 5 by adherence reported at day 5 ($\leq 75\%$ versus $> 75\%$).

II. Secondary outcomes

- a. Secondary outcomes for incidence will be presented as proportions and compared between the treatment groups with Fisher’s Exact tests.
- b. Symptom severity scores were recorded with the online participant surveys at days 3, 5, 10 and 14 only for those who responded “yes” to “Any symptoms experienced”.

- i. Visual analog scale (0-10) for “overall symptom severity” is collected via a digital slider bar, which is marked with “0 = no symptoms”; 5 (placed in the middle); and “10 = severe symptoms”

Severity of overall symptoms?

Please click to move the slider, even if your symptoms are a 5

* must provide value

0 = No symptoms 5 10 = Most severe

- ii. For those who responded “no” to “Any symptoms experienced” the symptom severity score for that visit is assigned as zero.
- iii. For those hospitalized or with deaths, their symptom severity was scored as 10 if they did not respond to the visit survey.
- iv. Analysis is by Kruskal Wallis tests among those with symptoms at day 14.

Clarifications (24 May 2020):

- Participants with missing outcome data are still included in the denominator, as the trial is performed as an intent to treat analysis.
- Sensitivity analyses were performed excluding participants with missing data from the denominator as well as including participants with missing data as events.

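### SAP II.b.iv compares day-14 severity only among participants with symptoms, without the whole-cohort symptoms yes/no test that protocol 11.4 puts first at Day 5

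*Combined protocol and SAP*

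**What the plan says.** Protocol 3.2.2 lists among the secondary outcomes "Symptom severity on day 5 or 14 via visual analog scale", and the protocol Summary lists the same endpoint.

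SAP II.b sets out the scoring and the test:

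- II.b.ii, for a participant who reports no symptoms at a visit: "the symptom severity score for that visit is assigned as zero".
- II.b.iii: "For those hospitalized or with deaths, their symptom severity was scored as 10 if they did not respond to the visit survey".
- II.b.iv: "Analysis is by Kruskal Wallis tests among those with symptoms at day 14".

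Protocol 11.4 (Secondary Analyses) has a two-step plan for Day 5. Symptoms yes/no is compared first by Fisher's exact test. The 0-10 score is then compared among those with symptoms. Neither 11.4 nor SAP II.b writes the first step for day 14.

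Two related whole-cohort provisions exist. Protocol 3.2.2 includes "Incidence of symptoms compatible with COVID-19 (possible disease" as a secondary outcome, and SAP II.a says "Secondary outcomes for incidence will be presented as proportions and compared between the treatment groups", by Fisher's exact test. The SAP clarification of 24 May 2020 adds: "Participants with missing outcome data are still included in the denominator, as the trial is performed as an intent to treat analysis".

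**The concern.** Having symptoms at day 14 is a post-randomization state. Protocol 2.2 hopes the drug will prevent disease or soften it, and either would change who is in the subset. The symptomatic participants in the two arms are therefore not comparable by randomization, and the zeros assigned in II.b.ii play no part in the test.

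Two things follow if the subset result is read alone. It carries no information on whether fewer people on the drug have symptoms at day 14. And if the drug removes mainly mild cases without lowering the other scores, the cases left in its arm are more severe on average, so the comparison can favour placebo although nobody was made worse.

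Two definitions are also open. The phrase in II.b.iv could mean symptomatic at the day-14 visit or at any time up to it. And it is not said whether hospitalized or dead non-responders scored 10 count as having symptoms.

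**Working it through.** **Inputs from the documents.** 750 per arm, up to 20% loss to follow-up and two-sided alpha 0.05 (protocol 11.2); the scoring rules in SAP II.b. The plan gives no sample size or power for the severity test. Its nearest figure is 621 per arm for 10% versus 5% (protocol 11.2, Table 1). The two-proportion formula gives

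n = [1.960·√(2·0.075·0.925) + 1.282·√(0.10·0.90 + 0.05·0.95)]² / 0.05² ≈ 581.1, rounded up to 582.

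With the continuity correction, (n/4)·[1 + √(1 + 4/(n·0.05))]² ≈ 620.4, rounded up to 621. Table 1 therefore reproduces.

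**Assumptions not in the documents.** Neither the share symptomatic at day 14 nor the score distribution is given. The column "Estimated transmission rate with placebo" in Table 1 (10-15%) is incidence over follow-up, so it fits only the reading of ever symptomatic by day 14. For symptomatic at that visit, 2.5% and 5% may be nearer. I used 600 per arm (750 × 0.8), scores among the symptomatic uniform from 0.5 to 9.5, and no participant made worse.

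**Direction, by exact arithmetic.** Suppose the drug clears half of the cases scoring below 4 and changes nothing else.

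- Share of cases below 4: 3.5/9 = 0.389, mean 2.25. Share above: 5.5/9 = 0.611, mean 6.75.
- Share cleared: 0.5 × 0.389 = 0.194. Share left: 0.806.
- Mean among the symptomatic: placebo 5.00; drug (0.611 × 6.75 + 0.194 × 2.25)/0.806 = 5.66.
- Whole-cohort mean at 10% symptomatic: placebo 0.10 × 5.00 = 0.50; drug 0.0806 × 5.66 = 0.456.

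The subset mean rises while the cohort mean falls.

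**How often the subset test would then favour placebo.** Simulation with 5,000 trials per cell (2,000 for the row marked *), tie-corrected Mann-Whitney (equal to two-group Kruskal-Wallis). Percentage of trials significantly favouring placebo; nominal 2.5%.

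| Drug effect | 2.5% symptomatic on placebo | 5% | 10% | 15% |
|---|---|---|---|---|
| Half of scores below 4 cleared, others unchanged | 9 | 14 | 26 | 37 |
| A quarter of scores below 4 cleared, others unchanged | 5 | 6 | 9 | 10 |
| Clearance falling linearly from 50% at the lowest score to 0 at the highest | 7 | 10 | 17 | 21 |
| Half cleared, remaining scores 10% lower | 3 | 3 | 4 | 4 |
| Half cleared, remaining scores 0.5 points lower | 4 | 4 | 5 | 6 |
| Half of all cases cleared, unrelated to severity | 2.4 | 2.5 | 2.3 | 2.5 |
| All scores down 1 point, lowest become symptom-free* | 0.8 | 0.3 | 0.1 | 0.2 |

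With a right-skewed distribution (0.5 + 9·Beta(2,4)) the first row becomes 10 / 16 / 30 / 42, and with remaining scores also 10% lower it becomes 3 / 5 / 6 / 7. Smaller repeat runs of the first row gave 34-36% in the last cell, so its second digit is not firm.

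**What the counts would show.** In the first-row trials that favoured placebo, the drug arm had fewer symptomatic people in 64 / 77 / 87 / 93%, but Fisher's test on those counts was significant in only 4 / 9 / 17 / 29%. The counts and an interval are therefore needed as well as a p-value.

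**Occurrence.** In a separate run with 621 per arm, the drug halves symptoms and severity among cases is equal. The subset test rejects in about 5% of trials; Fisher's test of yes/no rejects in about 91% at 10% versus 5%, 69% at 6% versus 3%, and 36% at 3% versus 1.5%.

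**The case against.** Several arguments limit the point.

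- **Occurrence of illness is tested elsewhere.** The prophylaxis primary endpoint and compatible symptoms are whole-cohort incidence endpoints with Fisher's exact test. If the subset means ever symptomatic by day 14, the incidence test is close to the missing step and little gap remains. This stands as a partial offset. On the at-that-visit reading it does not close the gap, because incidence over follow-up is not symptom status at day 14.
- **No rule is broken.** A reader might infer that the SAP drops a test the protocol requires. The protocol's yes/no step is written for Day 5 only, the SAP does not withdraw it, and the protocol's own second Day 5 step conditions on symptoms too. This stands in full: it is a choice of analysis that could be better, not a breach.
- **Reversal needs a narrow mechanism.** Protocol 2.2 hopes for milder disease. When scores fall across the board, the subset test favours placebo less often than the nominal rate. This stands. Deleting exactly the mildest half of cases, with nothing else changed, gives 99% at 10% versus 5%, but that is an extreme construction and carries no weight.
- **Not rejecting when severity among cases is equal is no defect.** That is how a test of severity among cases should behave. What remains is that such a result, read alone, could be taken as no effect on day-14 symptoms.
- **A rank test on all participants adds almost nothing.** It is mostly ties at zero. In the first scenario at 10% it favours the drug in 19% of trials, the same as Fisher's test. For a pure 25% fall in scores at 5 / 10 / 15% symptomatic it has 3 / 4 / 5% power, against 46 / 75 / 91% for the planned test. This stands: the planned test should be kept and the all-participant one is not needed.

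**Conclusion.** The concern holds in a limited form and is low priority. SAP II.b.iv plans a comparison in a subset formed after randomization and does not pair it with the day-14 yes/no comparison that would make it interpretable.

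The risk of a result favouring placebo is illustratively 9-14% at 2.5-5% symptomatic and 26-37% at 10-15%, but only if mild cases are selectively cleared and other scores stay put. It is about 3-4% if remaining scores also fall 10% (up to 7% with skewed scores), and at or below nominal if clearance is unrelated to severity or all scores shift down. All of this depends on assumed day-14 prevalence and score distributions.

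A reader might go further and conclude that the trial's efficacy conclusions are at risk. The documents do not support that. The prophylaxis primary analysis is a whole-cohort incidence comparison. The symptomatic cohort's primary mixed model (protocol 11.4) already uses zeros for the symptom-free and 10s for the hospitalized or dead. What is left is one secondary endpoint, mainly in the exposed cohort.

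**What to change.** In SAP II.b.iv:

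1. Add Fisher's exact test of symptoms yes/no at day 14 in the whole cohort. Report the counts by arm and a confidence interval for the difference. Handle missing responses as in the 24 May clarification: keep them in the denominator, with sensitivity analyses that exclude them and that count them as events.
2. Keep the symptomatic-only Kruskal-Wallis test. Label it as conditional on a post-randomization state, to be read only together with the yes/no result.
3. State whether the subset means symptomatic at the day-14 visit or ever by then, and whether non-responders scored 10 under II.b.iii belong to it. Use the same rule in both tests.

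The cost is a few lines of SAP text and one short extra secondary analysis on data already collected. Fisher's test will often be inconclusive when few people have symptoms, which is why the counts and interval should be shown.

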
Statistical Assumptions
	
 • 10% attack rate for close contacts (or 10% progression of disease to hospitalization among those symptomatic at entry) • Comparison of Proportions by Fisher’s Exact test for disease incidence; • Comparison of ordinal scale of disease severity by proportional odds model • N=621 sample per arm has 90% power to detect a 50% relative risk reduction (i.e. $\leq 5.0\%$) in disease incidence or 50% decrease in the ordinal disease severity (to $\leq 4.25\%$ disease incidence and $\leq 1\%$ hospitalization). • 20% dropouts, inflates sample size to n=750 per arm

Schematic of Study Design:

If hospitalization occurs, this SAE will be followed for up to 90 days

For participants who develop symptomatic disease, they will be followed for up to 90 days to assess final outcome status in the event of hospitalization.

Stratification is based on symptom status at baseline

1. 1500 asymptomatic healthcare workers or household contacts exposed to COVID-19
2. 1500 symptomatic COVID-19 outpatients

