11.4 Final Analysis Plan

Primary outcome analyses (intention to treat):

Asymptomatic Cohort Primary Analysis:

Those with asymptomatic exposure: Incidence of COVID 19 disease by day 14 will be assessed via Fisher's Exact Test.

Symptomatic Cohort Primary Analysis:

Those with symptomatic disease at study entry: For a summary metric of the change in symptom severity over 14 days, a longitudinal change over time repeated measures mixed-regression model will estimate the treatment effect by study arm. Subjects without symptoms are coded as a zero severity. Persons hospitalized or dead are coded as 10 severity.

Participants who become symptomatic with COVID19 on Day 1 before receiving the study medicine will be described with the symptomatic cohort.

Secondary Analyses:

For the asymptomatic with exposure cohort, the primary analysis (intention to treat) will be repeated for participants who received at least one dose of the study medicine.

- Secondary endpoints will be assessed via Fisher's Exact test and median (with interquartile ranges) as appropriate.
- Those with symptomatic disease at study entry: Proportional odds models will be used to assess the ordinal scale for disease severity at day 14 (illness without hospitalization, hospitalization without ICU stay or death, or hospitalization with ICU stay or death).
- Severity of overall symptoms at Day 0, 1, 5, and 14 is recorded on a 0-10 visual analog scale. Severity of symptoms at Day 5 will be compared first as a categorical analysis (no symptoms vs. symptoms) via Fisher's Exact Chi Square.
 - Second among those with symptoms, the 0-10 visual analog scale severity data will be compared via independent two-sample *t* test. If data are non-normally distributed, then data will be compared via Mann-Whitney U by study arm.

A priori subgroup analyses will include assessment by:

- Confirmed SARS-CoV-2 disease or disease exposure
- Healthcare worker vs. Household contact
- Days from Exposure
- Decile of age
- Sex as a biological variable
- Censored subjects, who became symptomatic before receipt of the first dose of study medicine on D#1, will be separately analyzed and reported.

Handling of withdrawn subjects.

If there is a large lost to follow up / study discontinuation rate, then the primary endpoint for the asymptomatic cohort would have a secondary analysis to assess incidence as a 3-category analysis of: i) no disease, ii) incident disease, or iii) unknown.

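### No planned missing-data analysis lets the outcomes of missing participants differ by arm, and the check that counts them all as events is dominated by losses when loss is high

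*Combined protocol and SAP*

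**What the plan says.** The SAP's Clarifications (24 May 2020) keep participants without an outcome in the denominator of the primary comparison, which in effect scores them as free of disease. Two sensitivity analyses follow: "excluding participants with missing data from the denominator as well as including participants with missing data as events". No distinction by arm is stated for any of the three rules.

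Protocol section 11.4, under the handling of withdrawn subjects, adds a further analysis that is conditional: "If there is a large lost to follow up / study discontinuation rate". It would then tabulate the asymptomatic cohort in three classes, one of them for unknown status. The threshold for a large rate is not given.

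The loss the plan allows for is in section 11.2: "Assuming 90% power, a two-sided alpha = 0.05 and loss to follow-up up to 20" per cent. The Summary carries the same allowance into the sample size: "20% dropouts, inflates sample size to n=750 per arm". Neither document gives an expected loss by arm.

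**The concern.** A sensitivity analysis for missing outcomes should show how far the assumption about the missing must move before the conclusion changes. For a two-arm comparison, the movement that matters most is a difference between arms: the missing on drug faring worse, or better, than the missing on placebo. None of the planned analyses explores this.

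The all-events check has a second weakness. It adds every loss to the event count, and the plan's loss allowance (20%) is larger than its placebo event rate (10%). When loss is high, most counted events are then unanswered surveys and the drug contrast is diluted. When loss differs between arms, the difference in loss enters directly as a difference in disease. At stake is whether a reader could wrongly call a real effect fragile, or read a loss imbalance as benefit or harm.

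**Working it through.** **Inputs from the plan.** Placebo rate: "10% transmission rate from COVID-19 cases to close contacts". Effect and evaluable size: "N=621 sample per arm has 90% power to detect a 50% relative risk reduction", that is 10% vs 5%. Allocation: "750 in placebo, 750 in intervention". Two-sided alpha 0.05 and Fisher's exact test (sections 11.2 and 11.4).

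**Assumptions.** Missing participants have the same true risk as observed ones in their arm. Interim looks are ignored. Loss by arm is not in the documents, so unequal loss is shown as a range.

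**The plan's own figure.** The uncorrected two-proportion formula gives n' = (1.96√(2×0.075×0.925) + 1.2816√(0.09+0.0475))² / 0.05² = 581.1, or 582 rounded up. The continuity correction gives n = (n'/4)(1+√(1+4/(n'×0.05)))² = 620.5, or 621, matching Table 1. With 750 per arm and 20% loss, 750×0.8 = 600 per arm are observed.

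**Expected counts at 20% loss in each arm, 10% vs 5%.** Missing: 150 per arm. Observed events: 60 vs 30.

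- Complete case: 60/600 vs 30/600, p=0.0014.
- Missing as non-events: 60/750 vs 30/750, p=0.0015.
- All-events: 210/750 vs 180/750, p=0.088.

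Losses make up 150/210 = 71% of the counted placebo events and 150/180 = 83% of the counted drug events.

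**Power under a true halving, equal loss.** With loss L and risk p, the all-events rate is L + (1−L)p on 750 per arm. Complete case uses p on 750(1−L). Powers are by exact enumeration of Fisher's test.

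| Loss, each arm | All-events rates | Ratio | All-events power | Complete-case power |
|---|---|---|---|---|
| 5% | 14.5% vs 9.75% | 0.67 | 79% | 94% |
| 10% | 19.0% vs 14.5% | 0.76 | 62% | 93% |
| 15% | 23.5% vs 19.25% | 0.82 | 49% | 92% |
| 20% | 28.0% vs 24.0% | 0.86 | 40% | 90% |

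If loss were 15% on placebo and 20% on drug (assumed), the all-events rates would be 23.5% vs 24.0%. A significant result favouring the drug would then occur in about 1% of trials, against 91% for complete case.

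**Rejection with no drug effect (10% in both arms).**

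| Loss, placebo / drug | All-events rates | All-events rejects | Complete case rejects |
|---|---|---|---|
| 20% / 20% | 28.0% vs 28.0% | 4.4% | 4.0% |
| 18% / 20% | 26.2% vs 28.0% | 11% | 4.5% |
| 15% / 20% | 23.5% vs 28.0% | 49% | 4.5% |
| 10% / 20% | 19.0% vs 28.0% | 98% | 4.5% |

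More loss on drug makes the drug look harmful. Reversing the 15% / 20% split gives the same 49%, now as an apparent benefit.

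**What an arm-specific table would show.** Take 20% loss in each arm and the expected observed counts. Significance is first lost at these points:

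| Event rate among missing placebo | Events among the 150 missing on drug | Comparison | p |
|---|---|---|---|
| 0% | 11 (7.3%) | 60/750 vs 41/750 | 0.063 |
| 10% | 23 (15.3%) | 75/750 vs 53/750 | 0.052 |
| 20% | 36 (24.0%) | 90/750 vs 66/750 | 0.051 |

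In the middle row, missing placebo participants behave like observed ones. Missing drug participants would then need about three times the 5% risk of observed drug participants before significance is lost. The planned rules that assign an outcome visit only two corners of this grid: 0% in both arms and 100% in both arms.

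**The case against.** Taken together, the SAP's three rules treat the missing as 0% events, as excluded and as 100% events, a familiar bracketing. The complete-case analysis is a good check: it keeps at least 90% power in every equal-loss row and its error rate stays below 5%. A reader might infer that the sensitivity analyses as a set can neither support nor undermine the primary result. The documents do not support that, because the fault lies in the all-events check alone.

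The 20% figure is an upper allowance, and actual missingness may be lower. Surveys go out on days 1, 3, 5, 10 and 14. Section 8.2 seeks permission to contact providers or public health authorities about participants lost to follow-up, and section 3.2.2 allows verification from records. At 5% loss the all-events check keeps about 79% power.

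A reader might also infer that the all-events rule generates false positives in general. It does not: with equal loss it rejects in about 4% of null trials. A false signal needs unequal loss, and participants are masked. Section 5.3.1 does say the products are not identical and section 2.3.1 lists side effects of the drug, so unequal loss is possible, but neither passage gives its size.

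The unknown category in section 11.4 would make a loss imbalance visible. That stands, but the analysis is conditional on an undefined rate and does not say what the unknown outcomes would have to be to change the conclusion.

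Finally, the SAP attaches no significance threshold to its sensitivity analyses. The power and rejection figures here measure how the check behaves; they are not a predicted decision.

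**Conclusion.** The point holds in limited form. No planned analysis lets the outcomes of the missing differ by arm, so the plan cannot show what imbalance would overturn the primary result. The all-events check adds little when loss is high: at 20% in each arm its power for the design effect is about 40%, against about 90% for complete case. Under no effect it misleads only if loss differs by arm, with rejection of about 11%, 49% and 98% at assumed gaps of 2, 5 and 10 points. These figures rest on the plan's 10% and 5% rates, 750 per arm and a stand-alone Fisher test at 5%. The complete-case figures also rest on missingness unrelated to outcome within arm. The primary test and the sample size are not called into question. This is an inexpensive improvement the sponsor should make.

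**What to change.** Keep the complete-case analysis and the declared all-events result. The SAP describes both as already performed, so they should not be withdrawn. Then:

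1. Label the all-events result a bound on absolute incidence, not a test of the drug.
2. Report the number with missing outcomes in each arm beside every version of the primary result.
3. Add a tipping-point table that varies the event rate among the missing separately in each arm (for example 0% to 30%), marks where the two-sided Fisher p-value crosses 0.05, and states whether those combinations are plausible given the loss in each arm. Date the addition so that readers can see it came after the Clarifications.

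The cost is an SAP addendum and a short program. It needs no new data and no additional participants.
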